8.7.2.1 Analysis of primary endpoint

The main growth evolution endpoint is defined as the change in height Standard Deviation Score (SDS) between baseline and the end of follow-up or GH, whatever occurs first. It will be described overall and depending on the duration of Norditropin[®] treatment.

Height SDS is defined as the deviation of patient's height from the standard French growth curve (normal values). It is obtained from the patient's height by subtracting the normal mean and dividing by the normal standard deviation.

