7.1 Primary objective

The primary objective is to describe the long-term change of height in children treated with Norditropin[®] for short stature due to NS over a 4-year period* in routine clinical practice in France.

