7.2 Secondary objectives

All secondary objectives (as follows) apply to children treated with Norditropin[®] for short stature due to NS:

- To describe the long-term safety profile of Norditropin[®]
- To describe the socio-demographic and clinical characteristics of patients
- To describe the therapeutic care of patients
 - Describe GH treatment patterns
 - Describe other NS treatments
- To describe the NS in terms of auxological characteristics, diagnosis, and NS comorbidities
- To describe the change in health-related quality of life (HRQoL) of patients and their parents /Legally Acceptable Representative (LAR)

* The follow-up period in this study is 4 years with possibility of extension for patients who did not reach adult height.

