8.1 Study design

This study is a PASS. This is a non-interventional registry of children treated with Norditropin® for short stature due to NS. This study aims to provide data on long-term growth evolution and safety of Norditropin® as well as HRQoL data. This registry will include the entirety of children treated with Norditropin® for short stature due to NS over the inclusion period. In consequence, this registry will enroll both patients who received Norditropin® before its marketing authorization for short stature due to NS in France and patients who received Norditropin® after its approval.

This study presents both a prospective and retrospective design. Data will be collected for 3 groups of patients:

- Incident patients: Children initiating Norditropin® upon their inclusion in the study.
- Prevalent patients:
 - Children who were already treated with Norditropin® before their inclusion in the study and finished their growth upon their inclusion. For these patients, all data will be collected retrospectively from medical records.
 - Children who were already treated with Norditropin® before their inclusion in the study and who did not finish their growth upon their inclusion. For these patients, data will be collected both retrospectively and prospectively.

HRQoL data will be collected on incident patients only.

The inclusion period will last for 24 months and patients will be followed-up for 4 years with possibility of extension for patients who did not reach AH. This will allow to provide interim results on October 2025 to the HAS.

All information will be collected as per physicians' routine of care and as this study is non-interventional, neither clinical interventions nor laboratory assessments will be imposed as per this protocol.

* The follow-up period in this study is 4 years with possibility of extension for patients who did not reach adult height.

[figure not shown]

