8.1.1.1 Primary endpoint

Table 2 Primary endpoint

Title of endpoint	Time frame	Unit
Change in height standard deviation score	From start of Norditropin® treatment until end of follow-up	SDS

The change in height in SDS (measured in scores -10 to +10) will be derived from recent national growth chart reference(2).

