AMH	Continuous variable	Endpoints
LH	Continuous variable	Endpoints
FSH	Continuous variable	Endpoints
Oestradiol	Continuous variable	Endpoints
Testosterone	Continuous variable	Endpoints
Auxology		
Gestational age at birth	Continuous variable	Endpoints
Head circumference at birth , at 1 year, 2 years and 3 years of age	Continuous variable	Endpoints
Birth weight, at 1 year, 2 years and 3 years of age	Continuous variable	Endpoints
Birth length at 1 year, 2 years and 3 years	Continuous variable	Endpoints
Weight at start of Norditropin®	Continuous variable	Endpoints

Variables	Operational Definition	Measurement
Height at start of Norditropin®	Continuous variable	Endpoints
Parents 'height	Continuous variable	Endpoints
BMI	Continuous variable	Endpoints
Height velocity in the first year/6 months preceding Norditropin® treatment start	Continuous variable	Endpoints
Height velocity	Continuous variable	Endpoints
Adult height (AH)	Continuous variable	Endpoints
Bone age	Continuous variable	Endpoints
Diagnosis		
Familial form of Noonan	Categorical variable 
 • Yes • No 	Endpoints
Parent affected (if yes to familial form of Noonan)	Categorical variant 
 • Mother • Father 	
Age at clinical diagnosis of NS	Continuous variable	Endpoints
Molecular diagnosis performed	Categorical variable 
 • Yes • No 	
Date of molecular diagnosis of NS (if yes to molecular diagnosis performed)	Continuous variable	Endpoints
Molecular diagnosis (type of NS-related genes mutated and variant identified)	Categorical variable 
 • PTPN1 • KRAS • RAF1 • RIT1 • SHOC2 • SOS1 • SOS2 • Other 	Endpoints
NS comorbidities		
NS comorbidities	Categorical variable 
 • Cardiac defects including pulmonary valve stenosis and hypertrophic cardiomyopathy • Orthopaedic issues (pectus, scoliosis) • Anorchia in males 	Endpoints
Therapeutic care		
Dose of Norditropin® treatment	Continuous variable Recorded at each study visit	Endpoints

Variables	Operational Definition	Measurement
Total duration of Norditropin® treatment	Continuous variable From start of Norditropin® treatment until end of follow-up	Endpoints
Total cumulative of Norditropin® dose	Continuous variable Total dose of Norditropin® administered from start of treatment until end of treatment	Endpoints

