8.7 Data analysis

8.7.1 Definition of analysis sets

The site populations will be defined as follows:

- Contacted sites: all reference and competence centres in France will be solicited to participate in this study
- Participating sites: all sites that agreed to participate in the study
- Active sites: all sites that included at least one eligible patient

The sites main characteristics (localisation, size) will be compared to ensure that the active sites are representative at the national level.

There are 3 patients population considered in this study:

- Overall population: all patients included in the eCRF,
- Full Analysis Set (FAS): all patients included in the eCRF and meeting all selection criteria. All secondary analyses will be performed on FAS.

- Growth Analysis Set (GAS): all patients from the FAS for which the primary criteria can be evaluated, i.e. height measurements available until the end of the 5-year follow-up or until NAH is reached, whatever occurs first.

The subgroups of interest for analyses are defined as follows:

- Norditropin[®] treatment duration: depending on age of onset and age at puberty onset, the patients may have shorter or longer time under GH treatment, which may highly influence auxological outcomes
- Mutated gene: PTPN11, SOC2, other

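### The primary endpoint is not tied to one time window, so the overall mean as written is not the 4-year height change in the objective

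*Protocol*

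**What the plan says.** The protocol describes the primary quantity in several places.

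- **Objective (7.1):** change in height "over a 4-year period* in routine clinical practice in France". The asterisk leads to a footnote: "The follow-up period in this study is 4 years with possibility of extension for patients who did not reach adult height".
- **Endpoint (8.1.1.1, Table 2):** "From start of Norditropin® treatment until end of follow-up". There is no 4-year cap.
- **Analysis (8.7.2.1):** the "change in height Standard Deviation Score (SDS) between baseline and the end of follow-up or GH, whatever occurs first". The abbreviation list gives GH as growth hormone, which is a substance and not an event.
- **Analysis set (8.7.1):** the GAS needs "height measurements available until the end of the 5-year follow-up or until NAH is reached, whatever occurs first". The abstract defines the same set by four years of follow-up or adult height. The last scheduled visit in Table 9 is M48.
- **Precision (8.5):** based on a change of 1.14 SDS after 4 years of treatment.

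The start point also varies. Section 8.2.8.2 labels the inclusion visit as baseline and counts the four years from it. Section 8.1 and Table 2 count from the start of Norditropin, and the Baseline column of Table 9 holds the height at Norditropin start.

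Section 8.1 defines three cohorts: incident, prevalent still growing, and prevalent children who had "finished their growth upon their inclusion. For these patients, all data will be collected retrospectively from medical records". The subgroups listed in 8.7.1 are treatment duration and mutated gene. Table 10 defines treatment duration as "Continuous variable From start of Norditropin® treatment until end of follow-up", and Table 5 uses the same time frame.

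**The concern.** Different readings of these passages give different numbers for the same child. If GH means the end of growth hormone treatment, a child who stops treatment before adult height is measured at the stop. If it is a slip for AH, the same child is measured later. A GAS requirement of 5 years admits different patients from one of 4 years.

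The larger issue is elapsed time. Measured from treatment start to the end of follow-up, incident patients contribute about 4 years and prevalent patients contribute whatever time has passed since they started. The overall mean then depends on the mix of cohorts and on calendar time, and it does not answer the 4-year question in the objective.

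The choice of clock also decides who can appear in the October 2025 interim report, because 8.7.3 refers the interim to the same definitions. First inclusion is March 2022, so 48 months after inclusion is reached in March 2026 at the earliest. With a clock from inclusion and the abstract's GAS, only patients already at adult height could enter that report's GAS. With a clock from treatment start, prevalent patients with 48 months of records could enter as well.

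**Working it through.** **1. The plan's own figures.** Inputs from 8.5: at most 50 eligible incident patients, at most 30 starts a year before 2020 from 2010 onwards (10 years), 79% of sites, 80% of eligible patients included, 80% evaluable, CV 20%.

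- Included: (50 + 30 × 10) × 0.79 × 0.80 = 221.2 (stated: 221).
- Evaluable: 221.2 × 0.80 = 177.0 (stated: 177).
- Precision: ε = 1.96 × 0.20 / √177 = 2.95% (stated: 2.95%). The other five cells of Table 11 also reproduce to rounding. On a mean of 1.14 SDS this is a half-width of 0.0295 × 1.14 = 0.034 SDS.

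The arithmetic is sound. The defect is in the definition of what is being averaged.

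**2. Cohort mix on those inputs.** Prevalent share: 300 / 350 = 86%. Evaluable incident: 50 × 0.79 × 0.80 × 0.80 = 25. Evaluable prevalent: 300 × 0.79 × 0.80 × 0.80 = 152. Both 50 and 30 a year are stated ceilings, so 86% is a ratio of ceilings and not an expected mix.

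**3. Elapsed time from treatment start, from the milestones in Table 1.**

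| Group | Span |
|---|---|
| Incident | 4 years; up to about 6 with extension (March 2022 to March 2028) |
| Prevalent, growth finished | at most about 14.2 years (January 2010 to March 2024) |
| Prevalent, still growing | at most about 18.2 years (January 2010 to March 2028) |
| Prevalent, still growing, started before 2020, four prospective years completed | at least about 6.2 years (end of 2019 to March 2022 is 2.2, plus 4) |

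Adult height may end any of these sooner. Children who started between 2020 and their inclusion are also prevalent under 8.1 and can have shorter spans. They are not in the count that reproduces 221.

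**4. The 5-year GAS against the timetable.** Five years after inclusion falls beyond the planned last visit (March 2028) for anyone included after March 2023. On a clock from inclusion, those patients would qualify only by reaching near adult height.

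**5. How far the overall mean could move.** This step needs an assumption, because the protocol gives no mean for prevalent patients. If their mean differs from the 4-year mean by a fraction x, the pooled mean shifts by 0.857x:

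| x | Shift of the pooled mean |
|---|---|
| ±10% | ±8.6% |
| ±20% | ±17.1% |
| ±30% | ±25.7% |

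The shift exceeds the stated precision once |x| is above 2.95% / 0.857 = 3.4%.

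**The case against.** **The footnote permits extension, and the authority asked for follow-up to adulthood (6.2).** Open-ended follow-up is therefore deliberate. That stands as a reason to collect and report the longer change. It does not supply a 4-year value.

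**GH is probably a slip for AH, and baseline can be read as treatment start.** On that reading Table 2 and 8.7.2.1 largely agree, so it would go too far to say that they cannot be reconciled. Neither would then give a 4-year change, and the two GAS definitions would still conflict.

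**Finished-growth patients.** A reader might infer that their change from inclusion is zero or undefined. The documents do not support this: 8.1 and Table 2 start these patients' data at Norditropin start, and Table 9 lists that height under Baseline.

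**Length of the spans.** A reader might also infer retrospective changes of up to 18 years. Wholly retrospective data stop at inclusion, at about 14 years. Eighteen is the calendar limit for retrospective and prospective data together.

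**The endpoint is also described by treatment duration.** This separates shorter from longer spans to some extent, and 8.7.1 gives a reason for the subgroup, so it should stay. It yields no 4-year estimate. Because duration runs to the end of follow-up, time off treatment counts as treatment; the adjacent cumulative-dose row in Table 10 stops at the end of treatment.

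**Cohort tables may be in the SAP.** That is possible, and 8.7.2 allows subgroup comparisons. The protocol should not be read as ruling them out. The weights in 8.7.2 address site activity and visit frequency, not elapsed time.

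**The registry is descriptive.** No test of the primary endpoint and no comparison with 1.14 SDS is planned. That limits the harm to the meaning of the reported mean and its stated precision.

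**Conclusion.** The point holds as a defect of definition. The protocol gives no single start and end point for its primary endpoint, and its primary analysis set is defined in two conflicting ways. Read as written, the overall mean combines about 4-year changes with changes of varying and often longer length. On the plan's ceilings, up to 86% of eligible patients are prevalent. The 2.95% precision was derived for a 4-year change and does not carry over to that mean.

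The counts, the precision figures and the calendar limits follow from the protocol. The size of any shift in the mean does not: it rests on an assumed difference between cohorts, in either direction, and is shown only to indicate that a small difference would exceed the stated precision.

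**What to change.** Reconcile the abstract, 7.1, Table 2, 8.7.1 and 8.7.2.1 to one definition:

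- **Primary endpoint:** change in height SDS from the last height at or before the first Norditropin dose to the height nearest 48 months after that dose, within a stated window, or to adult height if earlier. Replace GH in 8.7.2.1 accordingly and use one term for adult height.
- **GAS:** patients in the FAS with both of those heights, worded identically in the abstract and 8.7.1.
- **Secondary endpoint:** change from treatment start to adult height or last follow-up.
- **Reporting:** both endpoints overall and for the three cohorts in 8.1. Keep the treatment-duration subgroup.
- **Tables 5 and 10:** end treatment duration at the end of treatment, or at the end of follow-up if treatment is ongoing.

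The cost is wording in the protocol and the SAP. No new assessments are needed: the start date is recorded, and heights are collected about every six months, from treatment start for prevalent patients. The downside is that routine records may lack a height near 48 months for some retrospective patients (8.2.8.2 and 8.4 accept missing data), so the evaluable number may fall somewhat below 177. If it does not, 177 and 2.95% stand; at 150, Table 11 already gives 3.2%. Restricting the primary analysis to incident patients is not needed and would be costly: about 25 evaluable, with precision 1.96 × 0.20 / √25 = 7.8%.

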8.7.2.2 Analysis of secondary endpoint(s)

All secondary endpoints will be described according to the outputs defined in the statistical methods.

8.7.2.3 Analysis of exploratory endpoint(s)

Exploratory endpoints will be assessed through logistic regressions and mixed model. The models detailed characteristics and process will be described in the statistical analysis plan.

8.7.3 Interim analysis

Please refer to [8.7.2.1](#), [8.7.2.2](#), [8.7.2.3](#) and [8.7.4](#) sections

8.7.4 Sequential safety analysis/safety monitoring

All drug related adverse reactions (ADR), serious adverse drug reactions (SADR), serious adverse events (SAE) and adverse events (AE) will be classified and analysed from the initiation of the study drug until the end of follow-up.

Medical Dictionary for Regulatory Activities (MedDRA) version 19.1 or higher will be used for coding to "Lower Level Term (LLT)", "Preferred Term (PT)", "High Level Term (HLT)", "High Level Group Term (HLGT)" and the associated primary "System Organ Class (SOC)". CTCAE version 5 will be used to provide the grade.

AEs will be analysed as follows:

The number and percentage of patients experiencing:

- at least 1 on-treatment SAE/AE/SADR/ADR (including non-serious and serious irrespective of the relationship with the study treatment)
- at least 1 on-treatment SAE/AE/SADR/ADR related to the study treatment (including serious and non-serious AEs)
- at least 1 on-treatment serious SAE/SADR (regardless the relationship with the study treatment)
- at least 1 on-treatment serious SAE/SADR related to the study treatment
- at least 1 on-treatment SAE/AE/SADR/ADR leading to treatment discontinuation
- at least 1 on-treatment SAE/AE/SADR/ADR leading to treatment interruption/delay
- at least 1 on-treatment SAE/AE/SADR/ADR leading to dose decrease
- fatal on-treatment SAE/AE/SADR/ADR

They will be presented by SOC and preferred term.

Patient will be counted once by AE taking into account the maximum grade. The SOC/PT will be summarized (irrespective of the grade) and by maximum grade CTCAE (grade 1-2 ,3-4 and 5) as well. The incidence rate, corresponding to the number of patients experiencing at least one AE divided by the total person years of follow-up, will be calculated for each AE. A listing will be provided for fatal on-treatment AE. These analyses will be performed for the post-treatment AEs as well.

8.8 Quality control

Data entered in the eCRF will be verified as documented in the Data Validation Plan (DVP). The DVP will describe edit check specifications to ensure data accuracy and validity. A data review meeting will be set-up to resolve data inconsistencies that could not be addressed by the end of data collection. During this meeting, Novo Nordisk and [REDACTED] will agree on data management conventions. Database lock will occur once data review and all quality assurance procedures have been completed.

Data entered in the eCRFs that are transcribed from original documents must be consistent with the original documents or the discrepancies must be explained.

Audit

Novo Nordisk, its designees, IRBs/IECs or regulatory authorities may audit one or several study site(s), at any time during the study. The quality assurance auditor will have access to all medical records, the investigator's study-related files and correspondence, and the patient information documentation of this study to verify whether the study is being conducted in agreement with Good Pharmacoepidemiology Practices (GPP). The accuracy and integrity of data will also be verified by reviewing the study documents by focusing on key variables collected at each visit. The investigator will permit and provide direct access to all original documents.

8.8.1 Monitoring procedures

During the course of the study, monitoring should be performed to ensure that the protocol has been adhered to.

██████████ will perform routine remote oversight of the sites' data collection activities and periodic on-site monitoring visits with the aim to:

- Assess the progress of the study,
- Ensure adherence to study protocol,
- Discuss any emergency issues,
- Verify the eCRFs for accuracy and completeness,
- Validate the consistency of the eCRFs against the source documentation.

8.8.2 Critical documents

Before the physician starts the study (which is when informed consent is obtained from the first patient), the following documents must be available to Novo Nordisk or ██████████:

- Notification of the declaration to the French Data Protection Agency (CNIL)
- Documentation of the physician's qualifications as medically qualified (for instance a short CV or authorisation)
- Signed and dated agreement on the final protocol
- Signed and dated agreement on any amendment(s), if applicable
- Approval/favourable opinion from the Committee for Protection of Persons (CPP), clearly identifying the documents reviewed: the protocol including version, patient information form and any other written information to be provided to the patient
- Non-interventional study agreement
- Financial contract
- Source document agreement.

8.8.3 Retention of study documentation

Novo Nordisk will comply with Good Pharmacoepidemiology Practice (GPP) and relevant national legislation related to archiving of study documentation.

The physician must agree to archive the documentation pertaining to the study in an archive for at least 5 years after final report/first publication of the study, whichever comes later. The physician should not destroy any documents without prior permission from Novo Nordisk.

Novo Nordisk will retain the documentation pertaining to the study according to company procedure and in accordance with national regulations if they require a longer retention period.

8.9 Limitations of the research methods

As this is a non-interventional study, potential confounding factors cannot be ruled out. Data collection will reflect routine clinical practice rather than mandatory assessments at pre-specified time points, which may have an impact on the amount of data and its interpretation.

The following source of bias will be discussed:

- Selection bias
- Information (measurement) bias

8.9.1 Selection bias

Selection bias arises when the study population is not representative of the exposure or outcome pattern in the source population. Selection bias occurs both early during the recruitment of participants and later during the process of retaining the participants for the duration of the study. Registries are likely to be concerned by selection bias due to the fact that the inclusion of patients into a registry may be influenced by multiple factors such as clinical, demographic and socio-economic factors, notably in case the recruitment has not been exhaustive.

Sites' recruitment

All sites of the FIREENDO network will be contacted to participate in the study. We expect that approximately 80% of contacted sites will enrol patients into the registry, ensuring an acceptable representativeness of eligible sites. Still, sites representativeness of active sites (that include at least one eligible patient) will be compared to contacted sites to verify national representativeness (geographic location and activity size).

Patients' recruitment

This registry aims to enrol the entirety of patients treated with Norditropin® for short stature due to NS over the inclusion period and meeting the eligibility criteria. Both prevalent patients (children who were already treated with Norditropin® before their inclusion in the study) and incident patients (children initiating Norditropin® upon their inclusion in the study) will be included in the study.

To reduce the risk for physicians to influence patients' recruitment, we will provide them with clear instructions on the obligation of consecutive enrolment of patients. We expect that around 80% of eligible patients be included into the registry.

Attrition bias

This study will follow-up patients up to 4 years (with possibility of extension for patients who did not reach adult height) and as so is concerned by lost to follow-up. Attrition can threaten sample representativeness if characteristics of patients lost to follow-up differ from the other patients. To

minimize this bias, if a patient is lost to follow-up (due to change in the treating physician, moving up etc.), efforts will be undertaken to collect the data from the previous visit and physicians will be encouraged to contact the patient for AE information. Physicians will also complete a discontinuation CRF to document the reason(s) for discontinuation.

